Location of Study Site: (City, region/province/ state, country)	

Signature

Date (DD MMM YYYY)

SYNOPSIS

Name of Sponsor: ApoPharma Inc.	Individual Study Table Referring to Part of the Dossier Volume: Page:	(For National Authority Use Only)
Name of Finished Product: Deferiprone		
Name of Active Ingredient: 3-hydroxy-1,2-dimethylpyridin-4-one		
Title of study:	Long-term safety and efficacy study of deferiprone in patients with pantothenate kinase-associated neurodegeneration (PKAN)	
Study code:	TIRCON2012V1-EXT	
Phase of development:	Phase III	
Objectives:	
Primary: To evaluate the long-term safety and tolerability of deferiprone in patients with PKAN.
 
Secondary:
 
 • To evaluate the change in severity of dystonia over time in patients with PKAN treated with deferiprone. • To evaluate global improvement over time in patients with PKAN treated with deferiprone 	
Study design:	
Study TIRCON2012V1-EXT is an 18-month, multi-center, single-arm, open-label extension of study TIRCON2012V1. In the initial study, patients with a diagnosis of PKAN are being randomized in a 2:1 ratio to receive 18 months of treatment with either deferiprone or placebo, respectively. All participants who complete TIRCON2012V1 will be offered the opportunity to continue in the extension study, with the final visit (Week 78) of the initial study being considered Visit 1 of the extension study. (A 4-week follow-up visit that is planned for the end of study TIRCON2012V1 will be cancelled for individuals who choose to continue.)
 
Patients who were randomized to receive deferiprone in study TIRCON2012V1 will continue to receive deferiprone in the extension study, while those who were randomized to receive placebo will be switched to deferiprone. Since the initial study will still be in progress at the time that the first patients enter the extension study, patients and study staff will remain blinded as to which product was received for the previous 18 months.
 
In order to minimize the possible gastrointestinal upset that could result from starting deferiprone at too high a dose (and which might alert the former placebo recipients to the change in product), the dosing regimen will be titrated weekly for the first 3 weeks. All patients, including those who were on deferiprone initially, will receive 5 mg/kg deferiprone twice a day (b.i.d.) for the first week. If this dose is tolerated and there are no signs of toxicity, the dose will be increased to 10 mg/kg b.i.d. for the next week; and if that dose is tolerated, it will be increased the following week to 15 mg/kg b.i.d. for the remainder of the study. Individual dosages may be adjusted downward if necessary at any time for reasons of safety or tolerability.
	

Name of Sponsor: ApoPharma Inc.	Individual Study Table Referring to Part of the Dossier Volume: Page:	(For National Authority Use Only)
Name of Finished Product: Deferiprone		
Name of Active Ingredient: 3-hydroxy-1,2-dimethylpyridin-4-one		
Study design (cont'd):	Patients will have their hematology blood counts monitored weekly, and will undergo safety and efficacy assessments at 6 months (Visit 2), 12 months (Visit 3), and 18 months (Visit 4).	
Duration of participation:	The duration of participation in the extension study for each patient will be approximately 18 months.	
Criteria for evaluation:	
Safety:
 
 • Adverse events (AEs): Frequency, severity, time to onset, duration, and relatedness to study product • Serious adverse events (SAEs): Frequency, severity, time to onset, duration, and relatedness to study product • Number of discontinuations due to AEs • Hematology assessments • Blood chemistry assessments • ECG assessments 
Efficacy:
 
All patients:
 
 • Change in the Barry-Albright Dystonia Scale (BAD) total score from baseline (defined as prior to the start of deferiprone therapy) to Visit 4, as assessed by central evaluation of videotapes • Proportion of patients with improved or unchanged BAD scale total score between baseline and Visit 4 (responder analysis) • Change from baseline to Visit 4 in BAD scale score per body region (eyes, mouth, neck, trunk, and each upper and lower extremity), as assessed by central evaluation of videotapes • Change in score on the Patient Global Impression of Improvement (PGI-I) from Visit 1 to Visit 4 • Proportion of patients showing an improvement on PGI-I at Visit 4 (responder analysis) 
The time points for assessment of these efficacy endpoints are defined as follows:
 
 • For patients who received deferiprone in the earlier study, the baseline visit of that study will be treated as the baseline visit of TIRCON2012V1-EXT as well. Thus, Visit 1 of the extension study (Week 0) will be Year 1.5, and Visit 4 (Week 78) will be Year 3. • For patients who received placebo in the earlier study, Visit 1 of the extension study (Week 0) will be the baseline visit. Thus, Visit 4 (Week 78) will be Year 1.5. 	

Name of Sponsor: ApoPharma Inc.	Individual Study Table Referring to Part of the Dossier Volume: Page:	(For National Authority Use Only)
Name of Finished Product: Deferiprone		
Name of Active Ingredient: 3-hydroxy-1,2-dimethylpyridin-4-one		
Criteria for evaluation (cont'd):	
Only patients who received placebo in initial study:
 
For this group only, for each measure, the change seen between the start and completion of study TIRCON2012V1 (i.e., following 18 months on placebo) will be compared against the change seen between the start and completion of study TIRCON2012V1-EXT (i.e., following 18 months on deferiprone) as follows:
 
 • Comparison of change in BAD total score from baseline to completion of the initial study vs. change in BAD total score from baseline to completion of the extension study • Comparison of the proportion of patients with improved or unchanged BAD total score between baseline and completion of the initial study vs. the proportion with improved or unchanged BAD total score from baseline to completion of the extension study (responder analysis) • Comparison of the change in BAD score per body region between baseline and completion of the initial study vs. change in BAD score per body region between baseline and completion of the extension study • Comparison of change in PGI-I score from baseline to completion of the initial study vs. change in PGI-I score from baseline to completion of the extension study • Comparison of the proportion of patients showing an improvement on PGI-I at completion of the initial study vs. the proportion showing an improvement at completion of the extension study (responder analysis) 	
Number of patients:	A planned total of 90 patients will be enrolled in the TIRCON2012V1 study. All patients who complete that study will be invited to enroll in the extension study.	
Main criterion for inclusion:	Completed study TIRCON2012V1	
Investigational product:	Product: Deferiprone oral solution (80 mg/mL) Dose: Up to 15 mg/kg b.i.d. (based on tolerability) Mode of administration: Oral	

Name of Sponsor: ApoPharma Inc.	Individual Study Table Referring to Part of the Dossier Volume: Page:	(For National Authority Use Only)
Name of Finished Product: Deferiprone		
Name of Active Ingredient: 3-hydroxy-1,2-dimethylpyridin-4-one		
Schedule of treatment and specimen collection:	
All patients will be scheduled to take deferiprone daily, 2 times a day, for up to 18 months.
 
Safety and efficacy assessments will be conducted at the following time points:
 
 • Hematology: Weekly up to Visit 4 (End of Study) or early termination • Blood chemistry: Visits 1, 2, 3, and 4 or early termination • ECG: Visits 1 and 4 or early termination • BAD: Visits 1, 2, 3, and 4 or early termination • PGI-I: Visits 2, 3, and 4 or early termination * 
* The PGI-I will be conducted at Visit 1 as well, but its data on that day will be applicable only to the initial study (for which this is the last visit), not to the extension study.
	
Statistical methods:	
Safety Analysis
 
The incidences of AEs and SAEs reported during deferiprone therapy for all patients, from the start of TIRCON2012V1 to the completion of TIRCON2012V1-EXT, will be tabulated. Similar tables will be produced for the severity of AEs and for their relationship to the study medication. Time to onset and duration of all AEs with an incidence of >5%, and of any AEs of special interest (e.g., worsening of dystonia), will be summarized with descriptive statistics.
 
The percentage of discontinuations due to AEs will be calculated, and the AEs leading to discontinuation will be summarized in a frequency table by preferred term.
 
Laboratory data (hematology and blood chemistry) will be summarized using descriptive statistics for continuous variables and frequency tables for discrete variables. The incidences of out-of-range data will be tabulated, and the changes from baseline to the end of study will be examined using shift tables.
 
Efficacy Analysis
 
For the efficacy measures of BAD (total score and by body region) and PGI-I, the change from baseline to each of the measurement time points will be determined and summarized using descriptive statistics. A paired t-test will be used to assess the statistical significance of the changes in these efficacy outcomes from baseline to Visit 4. For the BAD total score and for PGI-I, the proportions of patients determined to be responders at Visit 4 will be calculated and presented along with 95% confidence intervals.
	

Name of Sponsor: ApoPharma Inc.	Individual Study Table Referring to Part of the Dossier Volume: Page:	(For National Authority Use Only)
Name of Finished Product: Deferiprone		

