1.2 Rationale

ApoPharma Inc. is currently conducting an 18-month trial, TIRCON2012V1, to assess the safety and efficacy of deferiprone in patients with PKAN. In that study, a planned 90 participants are being randomized in a 2:1 ratio to receive either deferiprone oral solution or placebo. Patients are scheduled to undergo weekly monitoring of absolute neutrophil count (ANC) and to undergo safety and efficacy assessments at Months 1.5, 3, 6, 12, and 18.

Patients who complete TIRCON2012V1 will be invited to enroll in the current study, in which all participants will receive deferiprone. Participants will thus receive deferiprone for a total of either 1.5 years or 3 years, depending on which treatment was assigned in the earlier study. The long-term data obtained will enable a better understanding of the use of deferiprone in this patient population.

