9 STATISTICAL ANALYSIS

9.1 Endpoints

9.1.1 Primary Endpoints

- Adverse events (AEs): Frequency, severity, time to onset, duration, and relatedness to study product

- Serious adverse events (SAEs): Frequency, severity, time to onset, duration, and relatedness to study product
- Number of discontinuations due to AEs
- Hematology assessments
- Blood chemistry assessments
- ECG assessments

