4.4.1 Adverse Events

A summary table of adverse events will include the following information:

- number of patients exposed to study treatment,
- number of patients experiencing at least one AE,
- number of patients experiencing at least one severe AE,

- number of patients experiencing at least one serious AE,
- number of patients experiencing at least one drug-related AE,
- number of deaths,
- total number of patients withdrawn,
- number of withdrawals due to AEs.

All adverse experiences will be coded using MedDRA (Medical Dictionary for Regulatory Activities) and will be summarized by MedDRA System Organ Class (SOC) and Preferred Term. Adverse events will be defined as: 1) AEs that occurred or worsened (increased in intensity and/or frequency) on or after the first dose of study medication, 2) AEs with a missing start date or a stop date on or after the first dose of study medication, 3) AEs with both a missing start and stop date. Events that occur within 14 days after treatment discontinuation will also be considered AEs. Serious adverse events that occur within 30 days after treatment discontinuation will be included in the database.

Adverse events will be summarized using the total number of AEs, the total number and percent of patients who experience an AE, and the number and percent of patients who experienced an AE within each SOC (and preferred term within an SOC). The rate of each AE (per 100 patient years) will also be calculated. AEs will also be presented by intensity (mild, moderate, severe), by seriousness (serious, non-serious), and by relationship to study medication (at least possibly related, not related). The number and percentage of patients who are withdrawn from the study due to AEs will be calculated, and the AEs involved will be summarized in a frequency table. Time to onset and duration of all AEs with an incidence of >5%, and of any AEs of special interest (e.g., worsening of dystonia), will be summarized with descriptive statistics.

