Cccccc	x (x.x)	x (x.xx)	x (x.x)	x (x.xx)
Cccccc	x (x.x)	x (x.xx)	x (x.x)	x (x.xx)
Cccccc	x (x.x)	x (x.xx)	x (x.x)	x (x.xx)
.....	x (x.x)	x (x.xx)	x (x.x)	x (x.xx)

Table 14.3.1.8 Summary of most common (>5%) adverse drug reactions – safety population

	DFP			
	Exposure (subject-years): x.xx			
	Total Subjects Exposed: xx			
	Total Events: xxx			
	Total Subjects Reporting: xx			
System Organ Class Preferred Term	N Subjects (%)	N Events (Rate/100 patient years)	Time to onset (Days) Mean (SD) Median (Min, Max)	Duration (Days) Mean (SD) Median (Min, Max)
CCCCC	x (x.x)	x (x.xx)	xx.xx (xx.x) xx.x (xx.x, xx.x)	xx.xx (xx.x) xx.x (xx.x, xx.x)
Ccccc	x (x.x)	x (x.xx)	xx.xx (xx.x) xx.x (xx.x, xx.x)	xx.xx (xx.x) xx.x (xx.x, xx.x)
.....	x (x.x)	x (x.xx)	xx.xx (xx.x) xx.x (xx.x, xx.x)	xx.xx (xx.x) xx.x (xx.x, xx.x)

Table 14.3.2.1.1 Hematology at each visit – safety population

Test	Visit	DFP (N=xx)
Hemoglobin (g/L) n Mean (SD) Median (Min, Max)	Baseline	xx xx.xx (xx.x) xx.x (xx.x, xx.x)
	Month 1.5	xx xx.xx (xx.x) xx.x (xx.x, xx.x)
	Month 3	xx xx.xx (xx.x) xx.x (xx.x, xx.x)
	Month 6	xx xx.xx (xx.x) xx.x (xx.x, xx.x)
	Month 12	xx xx.xx (xx.x) xx.x (xx.x, xx.x)
	Month 18	xx xx.xx (xx.x) xx.x (xx.x, xx.x)
	Month 24	xx xx.xx (xx.x) xx.x (xx.x, xx.x)

	Month 30	XX XX.XX (XX.X) XX.X (XX.X, XX.X)
	Month 36	XX XX.XX (XX.X) XX.X (XX.X, XX.X)
Repeat for other hematology parameters

Table 14.3.2.1.2 Hematology analysis: change in value at the end of study (Visit 4) – safety population

	Visit	n Mean (SD)	Change from Baseline n Mean (SD)	p-value [§]
Hemoglobin (g/L)	Baseline	xx xx.xx (xx.x)		
	Visit 4	xx xx.xx (xx.x)	xx xx.xx (xx.x)	0.xxxx
Repeat for other hematology parameters

§ p-value from paired t-test

Table 14.3.2.1.3 Shift table comparing three laboratory value categories at baseline and end of study: Hematology – safety population

Laboratory Test	Treatment	Baseline	End of study			Total
			Low	Normal	High	
Hemoglobin	DFP	Low	xx	xx	xx	xx
		Normal	xx	xx	xx	xx
		High	xx	xx	xx	xx
		Total	xx	xx	xx	xx
Repeat for other tests of interest						

Table 14.3.2.2.1 Blood biochemistry at each visit – safety population

Test	Visit	DFP (N=xx)
Seum Ferritin (ug/L) n Mean (SD) Median (Min, Max)	Baseline	xx xx.xx (xx.x) xx.x (xx.x, xx.x)
	Month 1.5	xx xx.xx (xx.x) xx.x (xx.x, xx.x)
	Month 3	xx xx.xx (xx.x) xx.x (xx.x, xx.x)
	Month 6	xx xx.xx (xx.x) xx.x (xx.x, xx.x)
	Month 12	xx xx.xx (xx.x) xx.x (xx.x, xx.x)
	Month 18	xx xx.xx (xx.x) xx.x (xx.x, xx.x)

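### Time to onset of adverse events, a component of the primary endpoint, is summarised only among affected patients and pools about 18 and 36 months of follow-up without censoring; for events at a roughly steady rate the result depends strongly on follow-up length

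*Protocol*

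**What the plan says.** Protocol 9.1.1 lists among the primary endpoints "Adverse events (AEs): Frequency, severity, time to onset, duration, and relatedness to study product", and repeats these attributes for SAEs. SAP 4.4 carries the same list.

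The planned analysis is one sentence, which appears in the protocol synopsis, protocol 9.4.1.4 and SAP 4.4.1. It covers "Time to onset and duration of all AEs with an incidence of >5%, and of any AEs of special interest", gives worsening of dystonia as an example of special interest, and says that these "will be summarized with descriptive statistics".

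The only shell that shows onset is SAP Table 14.3.1.8 (section 7), "Summary of most common (>5%) adverse drug reactions". Its onset column is headed "Time to onset (Days) Mean (SD) Median (Min, Max"), under a single DFP group.

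Follow-up on deferiprone differs by design. Protocol 1.2 states: "Participants will thus receive deferiprone for a total of either 1.5 years or 3 years", depending on the earlier assignment. SAP 3.5 starts the clock at first deferiprone exposure, in the initial study for continuers and in the extension for switchers. SAP 4.4 sets the safety period to match. SAP 3.2 gives 44 continuers and 24 switchers.

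SAP 3.5 bases safety analyses on observed cases. Neither document gives a Kaplan-Meier estimate, a cumulative-incidence estimate or a censoring rule for onset. SAP 4.4.1 does add an AE rate per 100 patient-years.

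**The concern.** An onset time exists only for a patient who had the event. A mean or median of onset times therefore conditions on the event having happened within that patient's observation period. When events arrive at a steady rate, the onset times of affected patients spread almost evenly over that period, and their mean falls near its midpoint. Here one group is watched for twice as long as the other, and the two are merged.

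A reader would take the table as showing when a reaction tends to appear after starting deferiprone. For a background or disease-related event, and possibly for worsening of dystonia in a progressive disease, the figure would largely describe the length of observation and the 44:24 mix. The planned rate per 100 patient-years corrects frequency for exposure but carries no information on timing.

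**Working it through.** The documents state no onset figure and no sample-size calculation, so there is no planned number to reproduce. The check models what the planned summary would report.

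**Inputs from the documents.** 44 continuers with about T = 36 months and 24 switchers with about T = 18 months (SAP 3.2, 3.5, 4.4). If all complete, this is 44 × 3 + 24 × 1.5 = 168 patient-years.

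**Assumptions, not in the documents.** First event per patient, no dropout, and the onset patterns below.

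**1. Constant rate.** With monthly hazard λ, the proportion affected by T is F = 1 − exp(−λT). Mean onset among affected patients is 1/λ − T·exp(−λT)/F.

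At 0.05 per patient-year, λ = 0.05/12 and 1/λ = 240 months.
- T = 18: exp(−0.075) = 0.9277 and F = 0.0723. Mean = 240 − 18 × 0.9277/0.0723, about 8.9 months.
- T = 36: exp(−0.15) = 0.8607 and F = 0.1393. Mean = 240 − 36 × 0.8607/0.1393, about 17.6 months.
- Expected affected patients: 44 × 0.1393 + 24 × 0.0723 = 7.86.
- The pooled median t lies below 18 months, so 68 × (1 − exp(−λt)) = 7.86/2. Hence 1 − exp(−λt) = 0.0578 and t = 14.3 months.

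The same steps at other rates give:

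| Events per patient-year | Mean, switchers (months) | Mean, continuers (months) | Pooled median (months) |
|---|---|---|---|
| 0.05 | 8.9 | 17.6 | 14.3 |
| 0.1 | 8.8 | 17.1 | 13.8 |
| 0.2 | 8.6 | 16.2 | 12.8 |
| 0.4 | 8.1 | 14.5 | 10.9 |

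An eightfold rise in rate moves the pooled median by 14.3 − 10.9 = 3.4 months. At a fixed rate, follow-up alone changes the group mean by a factor of 17.6/8.9 = 2.0 at the lowest rate and 14.5/8.1 = 1.8 at the highest.

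**2. Early cluster only.** The same formula applies within a susceptible subgroup with exponential onset.
- True mean 1 month: 1.00 in both groups.
- True mean 3 months: 2.96 and 3.00 (18 and 36 months of follow-up).
- True mean 6 months: 5.1 and 5.9.

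Up to a true mean of 3 months the groups agree within 0.05 month, so follow-up hardly matters.

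**3. Early cluster plus background.** Suppose 10% of patients are susceptible with mean onset 1 month, and background events reach 10% by 18 months. Then S(t) = (0.9 + 0.1·exp(−t))·exp(−λt), with λ = −ln(0.9)/18. Mean onset among affected patients is [∫₀ᵀ S(t) dt − T·S(T)]/[1 − S(T)].
- T = 18: 4.7 months, 19.0% affected.
- T = 36: 11.3 months, 27.1% affected.
- Pooled: (44 × 0.271 × 11.3 + 24 × 0.190 × 4.7)/(44 × 0.271 + 24 × 0.190), about 9.5 months. This describes neither process.

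**4. What a censored estimate would show.** With a constant hazard and 10% affected by 18 months, it gives 10% at 18 months and 1 − 0.9² = 19% at 36 months. The planned table would give a mean of 15.5 and a median of 14.1 months.

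**The case against.** The strongest reply is that onset among affected patients is a legitimate description of how soon an event came when it came. Frequency is a separate attribute with its own summaries, so onset need not respond to the event rate. That stands. It also means that the planned median should not be judged against the time by which half of all patients would have had the event, which is a different quantity and often would not be reached within 36 months. What remains is that the conditional summary depends on each patient's observation window, and two windows are pooled.

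A reader might infer that every onset figure is an artefact of follow-up, or that the table cannot separate early toxicity from steady background events. The documents and the check do not support this. Pure early clusters give nearly the same mean under either follow-up, and 1 month looks quite unlike 15. The protocol anticipates gastrointestinal upset on starting treatment, and the shell covers adverse drug reactions, where early onset is plausible.

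Three further points are fair:
- The study is single-arm and descriptive.
- The shell never displays the two groups side by side, so the twofold difference would be hidden in the pooled value rather than reported.
- The text says only descriptive statistics. Mean and median come from a shell that the SAP allows to change, and restriction to affected patients is inferred. It is, however, the only reading that fits the shell and the absence of a censoring rule.

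**Conclusion.** The point holds for events at a roughly steady rate and for preferred terms that mix an early cluster with background events. There the pooled onset figure depends strongly on follow-up length: a near twofold difference in group means at identical risk, and a 3.4-month shift in the pooled median over an eightfold range of rates. These sizes assume a constant rate, first events and no dropout.

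It does not hold for events clustered soon after the first dose, and it does not invalidate the primary safety evaluation as a whole. It is a weakness in one component, worth correcting because the correction is cheap.

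Two neighbouring limits belong with it. Table 14.3.1.8 covers adverse drug reactions above 5%, whereas the text promises all AEs above 5% and those of special interest, and no shell shows SAE onset. Also, the safety population requires a dose in the extension (SAP 3.3), so patients who left the initial study early on deferiprone are absent; censoring alone does not repair that.

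**What to change.** In protocol 9.4.1.4 and SAP 4.4.1, keep the descriptive summary, label its mean and median as conditional on having the event, and add the following:

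- For each AE above 5% and each AE of special interest, estimate the cumulative incidence of first occurrence from first deferiprone dose, with 95% CIs. Use Kaplan-Meier, or Aalen-Johansen with death as a competing event, and state which.
- Censor event-free patients at the end of the reporting window: last dose plus 14 days for AEs, plus 30 days for SAEs.
- Show the estimate by prior-treatment group, or over the common first 18 months. Do not present the groups as a treatment comparison.
- For events that force withdrawal, enter continuers into the risk set at extension Visit 1, since they could join the extension only after completing the initial study. This assumes that the initial study had a similar withdrawal rule; its protocol is not among the documents. For these events the first 18 months then rest on the 24 switchers.

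The change uses dates already collected. It costs SAP wording, some programming and one more table or figure per event type.
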